9.4 IGF-1 and IGF-1 SDS

IGF-1 will be listed for each patient, but not summarized. IGF-1 SDS will be listed, and summarized at each visit. In addition, the number and proportion of patients with IGF-1 SDS > 2 will be summarized. The denominator will be the number of patients with results at each visit. For the summaries of each 12 month period with multiple visits, each patient will be counted once, and will be counted as having IGF-1 SDS >2 if any results within that summarized interval is >2. IGF-1 SDS will also be summarized by ADA status.

9.5 IGFBP-3

IGFBP-3 levels will be provided in a listing.

9.6 Laboratory Test Results

Clinical laboratory measurements will be summarized with descriptive statistics at each visit. Changes within each 12 month period will use the first visit of the 12 month period as the baseline. For Period V the baseline will be the first visit with PEN injection. If data from the first visit of each period are not available, the last previous visit data will be used. Summary of abnormal results (reported as low, high, clinically significant) will be provided for each 12 month period, with the number of patients at the beginning of each period for the denominator.

The following laboratory results will be presented:

Glucose Metabolism	Endocrinology	Lipid Metabolism
Fasting blood Glucose	FT4	Cholesterol
Fasting Insulin	Т3	High density lipoprotein (HDL)
HbA1c	Thyrotropin (= TSH)	Low density lipoprotein (LDL) Cholesterol
	Cortisol, Free	Lipoprotein-A
	Females >=12 y.o.: FSH, LH and estradiol	Triglycerides
	Male >=13 y.o.: FSH, LH and testosterone	

Glucose Metabolism, Endocrinology, and Lipid Metabolism:

Clinical Chemistry	Hematology	Urinalysis
Albumin	Differential Blood Count of Leukocytes	Bilirubin
Alkaline phosphatase	Erythrocyte Count	Glucose
Calcium	Hematocrit	Ketones
Chloride	Hemoglobin	Leukocyte Esterase
Creatinine	Leukocytes	Nitrite
Gamma-glutamyl Transferase (GGT)	Mean Corpuscular Hemoglobin (MCH)	рН
Lactate Dehydrogenase (LDH)	Mean Corpuscular Hemoglobin Concentration (MCHC)	Protein
Phosphate	Mean Corpuscular Volume (MCV)	Specific Gravity
Potassium	Platelet Count	Urinalysis Blood
Serum Glutamic Oxaloacetic Transaminase (SGOT)		Urobilinogen
Serum Glutamic Pyruvic Transaminase (SGPT)		
Serum Iron and Transferrin		
Sodium		
Total Bilirubin		
Total Proteins		
Urea (blood urea nitrogen)		
Uric Acid		

• Chemistry, Hematology, and Urinalysis:

The increases in alanine aminotransferase (ALT), aspartate aminotransferase (AST), and total bilirubin will be examined for liver function. The count and percentage of the increases will be tabulated for each visit including baseline. The increases of ALT and AST will be examined in three categories, i.e. $>2 \times$ upper limit of normal (ULN), $>3 \times$ ULN, and $>5 \times$ ULN, and that of total bilirubin combined with ALT or AST increases will be examined in 1 category, total bilirubin $>3 \times$ ULN and ALT or AST $>2 \times$ ULN.

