8.5 SAFETY EVALUATION

The assessment of safety will be based mainly on the frequency of AEs, frequency of anti-MOD-4023 antibody development and on the number of laboratory values that fall outside of laboratory normal ranges. Other safety data (e.g. vital signs, special tests, etc.) will be considered as appropriate.

AEs will be listed by treatment group and patient for the treatment phase. AEs will be summarized by presenting, for each treatment group, the number and percentage of patients having any AE, having an AE in each body system and having each individual AE. Any other

OPKO Biologics	Protocol for Clinical Study CP-4-004	Page 97 of 133
Effective Date: Date of final electronic approval		

information collected (e.g. severity or relatedness to study medication) will be listed as appropriate.

Summaries and analyses will be based on treatment-emergent adverse events (TEAE), which are defined as AEs occurring after the first administration of study medication (as recorded on the study discontinuation / end of study CRF) or AEs present before the first dose and ongoing after administration with increased severity. Other AEs (pre-treatment AEs) will only be listed.

If appropriate, laboratory and/or ECG data will be summarized by presenting shift tables using extended normal ranges (baseline to most extreme post-baseline value), by presenting summary statistics of raw data (means, medians, standard deviations, ranges) and change from baseline values and by the flagging of notable values in data listings.

Blood glucose, HbA1c, cortisol, thyroid panel tests and lipid panel tests (with special attention on LpA) will be evaluated using standard descriptive statistics, the number of patients who had values outside normal values, and by listing values considered clinically relevant by the investigator.

Data from other tests (e.g. blood pressure or vital signs) will be listed, notable values will be flagged, and any other information collected will be listed as appropriate. Summary statistics will be given where appropriate.

In addition the number and percentage of patients developing antibodies, including neutralizing antibodies, will be summarized by cohort.

Local tolerability will be summarized based on the investigator's assessments of pain, tenderness, erythema, warmth and swelling which will be done by a scale and predetermined schedule during intensive PK/PD sampling.

The safety analysis will be performed based upon the safety analysis subset.

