9.8 Vital Signs

The vital signs (systolic / diastolic blood pressure in seated position, respiratory rate, pulse rate, and body temperature) will be summarized at each visit. The change from the beginning of OLE, and the change within each year for continuous parameters will be presented.

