10.3 Change in Height SDS

HT SDS will be summarized with descriptive statistics at the end of OLE years 1 - 4 and for each year on PEN. HT SDS will also be presented for each treatment year, including Period I and II, by the original treatment group assignment and total. In addition, HT SDS will be summarized by ADA status. Descriptive statistics will be used to characterize the change in HT SDS. The change in HT SDS will be calculated from baseline of Period I, as well as each 12 month period.

In addition, the cumulative change in HT SDS from the baseline at Period I will be calculated for each of the scheduled Month 12 visit of each year, using the original treatment groups assignment and total.

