11.2 Listings

Listing No.	Description
16.1.7	Randomization
16.2.1.1	Patient Disposition
16.2.1.1b	Patient Disposition - CP-4-004 OLE
16.2.1.1c	Listing of Patients final height as of last known visit in Study CP-4-004
16.2.1.2	Trial Inclusion/Exclusion Criteria
16.2.1.3	Inclusion/Exclusion Criteria Not Met
16.2.10	Comments
16.2.2	Protocol Deviations
16.2.4.1	Patient Demographics
16.2.4.2	Medical History at Start of Main Study
16.2.4.3	ACTH Test Results
16.2.4.4	MRI Results
16.2.4.5	Pubertal Status at Start of OLE (Year 1)
16.2.5.1	Patient Visits
16.2.5.2	Drug Accountability
16.2.6.1	Height, Height SDS, Change in Height SDS, and Height Velocity at Each Visit
16.2.6.1.b	Listing of antibodies and efficacy data in all patients in Study CP-4-004 OLE
16.2.6.2	Bone Age by Visit
16.2.6.3	Bone Maturation by Visit
16.2.7.1	All Adverse Events
16.2.7.2	All Serious Adverse Events
16.2.7.3	All Adverse Events Leading to Withdrawal from the Study
16.2.7.4	All Adverse Events of Special Interest
16.2.7.5	All Injection Site Reactions
16.2.8.1	IGF-1 and IGF-1 SDS Results at Each Visit
16.2.8.2	IGF-1 SDS > 2
16.2.8.3	IGFBP-3 Results at Each Visit
16.2.8.4	Glucose Metabolism Results
16.2.8.5	Endocrinology Results
16.2.8.6	Lipid Metabolism Results
16.2.8.7	Chemistry Results
16.2.8.8	Hematology Results
16.2.8.9	Urinalysis Results

Listing No.	Description
16.2.8.10	Pregnancy Test Results
16.2.8.11	Gonadotropic Hormone Results
16.2.8.12	MOD-4023 Serum Levels
16.2.9.1	Vital Sign Results by Visit
16.2.9.2	Physical Examination Results
16.2.9.3	Electrocardiogram Results
16.2.9.4	Concomitant Medications
16.2.9.5	Exposure and Duration of Treatment
16.2.9.6	Antibody Titers
16.2.9.6b	Antibody Titers (Anti-hGH Nab)
16.2.9.7	Injection Site Pain, Redness, Bruising, Swelling, and Itching Scores by Visit
16.2.9.8	Fundoscopy
16.2.9.9	Weight and Height at Each Visit
16.2.9.10	Pubertal Status by Visit
16.2.9.11	Summary of Dose Adjustments
16.2.9.12	Listing of antibodies to somatrogon and individual efficacy data in patients with CTP+ in Study CP-4-004 (Main and OLE)

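### SAP 9.6 plans laboratory change only within each 12-month period or from the first PEN visit; no cumulative same-child change or shift from a fixed baseline is planned, although long-term safety is the primary objective

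*SAP*

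**What the plan says.** SAP 9.6 begins with levels: "Clinical laboratory measurements will be summarized with descriptive statistics at each visit". It then defines change: "Changes within each 12 month period will use the first visit of the 12 month period as the baseline". For the pen period: "For Period V the baseline will be the first visit with PEN injection". If a period's first visit has no value, the last previous visit is used. Abnormal values are counted by period: "Summary of abnormal results (reported as low, high, clinically significant) will be provided for each 12 month period". The denominator is the number of children who start that period.

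SAP Section 11 gives each laboratory panel one table of results and one of abnormal results (14.5.1.1 to 14.5.6.2), a separate table of liver-test increases (14.5.7), summary figures, and per-child listings such as "Glucose Metabolism Results". No title refers to laboratory change from a fixed baseline or to a laboratory shift.

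Other sections of the SAP use a fixed reference. For vital signs, 9.8 asks for "The change from the beginning of OLE, and the change within each year". For height, 10.3 says "the cumulative change in HT SDS from the baseline at Period I will be calculated". Protocol 8.5 provides, if appropriate, for laboratory change from baseline and for "shift tables using extended normal ranges (baseline to most extreme post-baseline value". SAP Section 2 says that departures from the protocol's analysis will be recorded in the SAP. SAP 3.1.1 makes safety in extended treatment the primary objective.

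**The concern.** In Periods III and IV the reference value moves forward every year. After the first interval it is always an on-somatrogon value. For children from Cohorts 1 to 3 it is on-treatment even in the first OLE year, because they have already had 12 months of drug. An effect that builds slowly over years then appears as a series of small annual changes, and its total is not summarized for the same children.

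The tests affected include those the protocol singles out. Protocol 5.7.1.3 says the lipid effects of long-acting growth hormone have not been studied enough. Protocol 5.7.1.4 warns that treatment may unmask hypothyroidism. Protocol 5.8 names HbA1c and fasting glucose among the guides to dose decisions. In Period IV the routine safety laboratory panel is annual, apart from one check three months after a switch to 0.66 mg/kg/week, so a yearly change row is essentially one paired difference per child.

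The annual counts of abnormal results have a related limit: a child who is high in four successive years is counted in each, with no separation of new from pre-existing or persistent abnormality.

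**Working it through.** **Step 1. Which baselines are planned.**

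| Measure | Fixed baseline | Within-period change | Shift table |
|---|---|---|---|
| Height SDS (SAP 10.3) | Period I | Yes | n/a |
| Vital signs (SAP 9.8) | Start of OLE | Yes | None |
| ECG (Table 14.6.3.2) | n/a | Yes (Table 14.6.3.1) | Yes, by year |
| Laboratory (SAP 9.6) | None in Periods III-IV; first PEN visit in Period V | Yes | None |

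The laboratory row is the only one with neither a pre-OLE or OLE-start baseline nor a shift table.

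**Step 2. Do yearly changes lose the total?** Not in a complete cohort. If the same children are measured at every visit and each year's end is the next year's start, the mean annual changes add up to the mean cumulative change. In a simulated set (assumed: 53 children, 5 years, drift 0.05 per year, between-child SD 0.25, visit SD 0.2, starting level about 5.2) the annual means were 0.078, 0.036, -0.024, 0.174 and 0.024. They sum to 0.287 before rounding, and the mean cumulative change is also 0.287.

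A reader who adds the rows still lacks an interval for the total. Adjacent annual changes share a visit, so their errors are correlated. With independent visit errors of SD s, each annual change and the 5-year change all have SE s√(2/n). Combining five rows as if independent would give √5 = 2.24 times that.

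**Step 3. When children leave.** In the same simulated data, the four highest-value children were removed each year, leaving 33. Visit means rose from 5.159 to 5.356, that is 0.197. The mean same-child change in the 33 was 0.291. The visit means fell short by 0.291 - 0.197 = 0.094, about a third. This pattern is constructed to show the direction of the effect. The documents give 53 children entering the OLE and no rate of later loss.

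**Step 4. Scale.** The documents give no drift rate or laboratory SD, so all of the following are assumed. Let drift be d within-child SD per year, with independent visit errors and n children.

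- One annual change: z = d√(n/2).
- Change over K years: z = K·d√(n/2).
- Chance that a 95% interval lies above zero: Φ(z - 1.96).

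For n = 53, d = 0.1, K = 5: √(53/2) = 5.15, so z = 0.51 for one year and 2.57 over five.

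| n | d per year | One annual change | 5-year change |
|---|---|---|---|
| 53 | 0.1 | 7% | 73% |
| 53 | 0.2 | 18% | >99% |
| 53 | 0.3 | 34% | >99% |
| 30 | 0.1 | 6% | 49% |
| 30 | 0.2 | 12% | 97% |
| 30 | 0.3 | 21% | >99% |

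The K-fold gain in z is a favourable case. If a child's values moved as a random walk, the K-year SE would be √K times the annual SE and the gain would be K/√K = √5 = 2.24 at five years.

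**The case against.** The strongest reply is that nothing is hidden. Levels are summarized at every visit, abnormal values are counted, figures are planned and each child's values are listed. Glucose and thyroid impairment are adverse events of special interest over the whole extension (SAP 9.1), and dose changes are summarized by reason (SAP 9.13). A reader might infer from the yearly baselines that long-run drift is never measured. The documents do not support that. Suppose HbA1c rose 0.1 point a year from 5.4% in a constant 50 children (assumed values): the visit mean would reach 6.0% after six years in plain view. Setting that mean against the 6.2% figure in Protocol 5.8 would also mislead, because 6.2% applies to individual children.

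Two further strong readings fail. A reader might take Period V to be reset every year, but SAP 6 and 9.6 name one PEN baseline, so change may accumulate across PEN years; the wording does not settle it. A reader might also see a breach of the protocol, but 8.5 is conditional. At most, a foreseen display was dropped without the note that SAP Section 2 promises.

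Two limits also stand. This SAP covers only the OLE, and Main Study analyses belong to a separate plan that is not available here. Entry criteria exclude diabetes and impaired fasting glucose, so pre-existing abnormality should be uncommon for glucose.

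The gap remains. Visit means follow different children as some leave, and Protocol 4.6 and 5.7.1.2 allow withdrawal for abnormal laboratory values or impaired glucose metabolism. Under Protocol 7.1 an abnormal value is an adverse event only if it causes symptoms, is clinically significant or needs therapy, so drift below that level is not captured. Listings are data, not a planned summary.

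**Conclusion.** The point holds as a moderate reporting gap in a descriptive analysis. Laboratory levels are summarized, but cumulative same-child change and shift from a fixed baseline are not, for tests central to the primary objective. The SAP already uses fixed baselines for vital signs and height SDS.

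The omission follows from the text of SAP 9.6 and the titles in Section 11 and needs no assumption. Its size does: the 7% to 34% against 73% to over 99% (53 children, five years) rests on assumed drift of 0.1 to 0.3 SD per year and independent visit errors, and the loss in visit means on a constructed attrition pattern. No data are lost, and the cumulative change can still be derived.

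**What to change.** In SAP 9.6, keep the within-year change and add:

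- Same-child change at each annual visit, with the number of paired values and a confidence interval, from the start of OLE (as in SAP 9.8) and from the pre-somatrogon baseline. The latter is Period I Visit 1 for Cohorts 1 to 3, and the last value before the first somatrogon dose for former Genotropin children.
- Shift tables from the pre-somatrogon baseline to the most extreme on-treatment value for glucose, thyroid and lipid parameters, so that new abnormalities are separated from pre-existing ones.
- A sentence saying whether PEN years 2 onward use the first PEN visit or a new yearly baseline.

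The cost is SAP wording and a few tables. Protocol 5.1.2 schedules these tests at Visit 1 for all cohorts, so no new collection is needed. Lp(a) is not measured in the PEN period (Protocol 5.7.1.3), so its series ends earlier. The cumulative change stays descriptive: age, puberty and dose switches contribute to it, and there is no concurrent control after month 12. A table footnote should say so.

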4.1 INCLUSION CRITERIA

1. Pre-pubertal child aged \geq 3 years old and not above 10 years for girls or 11 years for boys, with either isolated GHD, or GH insufficiency as part of multiple pituitary hormone deficiency.
2. Confirmed diagnosis of GHD by two different GH provocation tests defined as a peak plasma GH level of █ ng/ml¹, determined by central laboratory using a validated assay². If the patient has already been tested locally and reserve samples that were taken at appropriate time-points are available, these will be reanalyzed by the central laboratory³. Historical tests missing the -30 minutes time point will be accepted. If no reserve samples are kept (only for tests performed prior to site initiation), then the details of the locally performed tests will be reviewed by the Coordinating Investigator: if the results cannot be accepted, the patient will undergo both stimulation tests during the screening period and the samples will be analyzed by the central laboratory. At least one of the two stimulation tests (and preferably both) will be analyzed by the central laboratory. If the patient requires sex hormone priming (due to the age), and both stimulation tests must be performed during the Screening (no historical samples kept, or test was without priming), it is recommended to perform stimulation tests in consecutive setting in one day, or in two consecutive days, to avoid priming the patient twice. Local historical tests without sex-steroid priming will not be accepted for patients that require sex steroid priming according to the protocol.
3. Bone age (BA) must be not older than chronological age, and should be no greater than 9 years for girls and 10 years for boys.
4. Without prior exposure to any r-hGH therapy.
5. Impaired height and height velocity defined as:
 - a. Height (HT) of at least 2.0 standard deviations (SD) below the mean height for chronological age (CA) and gender according to the standards of Prader et al. (1989) (HT SDS \leq -2.0);
 - b. Annualized height velocity (HV) below the 25th percentile for CA (HV $<$ -0.7 SDS) and gender according to the standards of Prader et al. (1989). The interval

¹ Patients will be divided into two subgroups: Patients with peak serum GH levels after stimulation test █ ng/ml and patients with peak serum GH levels after stimulation test █ and █ ng/ml.

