² Insulin tolerance test, with cortisol response to hypoglycemia if insulin stimulation test is chosen / Arginine test / Clonidine test / Glucagon test (plus or without propranolol) / L-dopa plus propranolol.

³ Central laboratory results will be used for eligibility confirmation.

OPKO Biologics	Protocol for Clinical Study CP-4-004	Page 42 of 133
Effective Date: Date of final electronic approval		

between two height measurements should be at least 6 months, but should not exceed 18 months prior to inclusion.

6. BMI must be within ± 2 SD of mean BMI for the chronological age and sex according to the 2000 CDC standards (www.cdc.gov/growthcharts).
7. Baseline IGF-I level of at least 1 SD below the mean IGF-I level standardized for age and sex (IGF-I SDS ≤ -1.0) according to the central laboratory reference values.
8. Children with normal fundoscopy (ophthalmoscopy) at screening (without signs/symptoms of intracranial hypertension as assessed by fundoscopy).
9. Children with multiple hormonal deficiencies must be on stable replacement therapies for other hypothalamo-pituitary-organ axes for at least 3 months and 6 months for thyroid replacement therapy prior to the first study drug administration.
10. Normal 46 XX karyotype for girls.
11. Written informed consent of the parent or legal guardian of the patient and assent of the patient for the Main Study and for the OLE.

Patients who completed the first year of treatment in the Main Study are allowed to enter the OLE. Patients who were off treatment for over [REDACTED] after completing the main study (or during the OLE) are allowed to participate/continue in the OLE after completing additional testing.

Specific inclusion criteria for Period V (LT-OLE –PEN):

12. Continuing participation in the LT-OLE-PEN period.
13. Signed consent and assent (when applicable) form for the LT-OLE-PEN period.
14. Investigator's assessment and confirmation of the patient anticipated compliance to the protocol procedures.
15. Agreement to refrain from sexual activity during the study i.e. observe complete sexual abstinence as the only acceptable contraceptive measure in this study.

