5.7.1.4 Hormonal status with special attention on thyroid and adrenal status

Cortisol: Blood cortisol should be monitored throughout the study since GH treatment may unmask previously undiagnosed or sub-clinical central hypoadrenalinism.

Supra-physiological glucocorticoid treatment may attenuate the growth promoting effect of somatropin (as for asthma). Therefore, children requiring a glucocorticoid dose of greater than 400 µg/d of inhaled budesonide or equivalents (approximately equivalent doses: Fluticasone: 264 µg/d; Beclomethasone: 504 µg/d; Flunisolide 1,000 µg/d; Triamcinolone: 1,000 µg/d) for longer than 1 month during a calendar year will not be included in the study or may be discontinued if additional dosing is required.

Thyroid hormones: Blood TSH and T4 should be monitored throughout the study since GH treatment may unmask previously undiagnosed or sub-clinical central hypothyroidism. Undiagnosed/untreated hypothyroidism attenuates growth and metabolism. Upon diagnosis of hypothyroidism, thyroid hormone replacement therapy should be initiated following approval by Coordinating Investigator. Thyroid dose should be adjusted throughout the study so that T4 levels will be close to the median range.

Gonadotrophic hormones - (applicable only for the LT-OLE and LT-OLE-PEN periods) - FSH, LH and Estradiol for females that are 12 years old and above and LH, FSH and testosterone for males that are 13 years old and above.

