5 ANALYSIS POPULATIONS (ANALYSIS SETS)

Since this is an OLE with patients from the primary study, all patients will be included in a single Full Analysis Set for reporting.

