14.4.2.2	Annualized Height Velocity on PEN by ADA Status: Full Analysis Set
14.4.2.3	Annualized Height Velocity (cm/yr) at End of Main Study, End of each OLE and PEN Year by ADA Status and Initial Cohort Assignment: Full Analysis Set
14.4.2.4	Height SDS at End of each OLE and PEN Year by ADA Status: Full Analysis Set
14.4.2.5	Height SDS at Baseline and End of Main Study, End of each OLE and PEN Year by ADA Status and Initial Cohort Assignment: Full Analysis Set
14.4.2.6	Annual Change in Height SDS at End of each OLE Year By ADA Status: Full Analysis Set
14.4.2.7	Annual Change in Height SDS at End of each PEN Year by ADA Status: Full Analysis Set
14.4.2.8	Cumulative Change in Height SDS at End of Main Study, End of each OLE and PEN Year by ADA Status and Initial Cohort Assignment: Full Analysis Set
14.4.2.9	Highest IGF-1 SDS During OLE and PEN Years by ADA Status: Full Analysis Set
14.4.3.1	Annual Incidence of Treatment-Emergent Adverse Events by SOC and Preferred Term by ADA Status: Full Analysis Set
14.4.3.2	Annual Incidence of Serious Treatment-Emergent Adverse Events by SOC and Preferred Term by ADA Status: Full Analysis Set
14.4.3.3	Annual Incidence and Severity of Treatment-Emergent Adverse Events by SOC and Preferred Term by ADA Status: Full Analysis Set
14.4.3.4	Annual Incidence and Relationship of Treatment-Emergent Adverse Events by SOC and Preferred Term by ADA Status: Full Analysis Set

Table No.	Description
14.4.3.5	Annual Incidence of Treatment-Emergent Adverse Events of Special Interest by Type and Preferred Term by ADA Status: Full Analysis Set
14.4.3.6	Overall Incidence of Injection Site Reactions by SOC and Preferred Term by ADA Status: Full Analysis Set
14.4.3.7	Annual Incidence of Injection Site Reactions by SOC and Preferred Term by ADA Status: Full Analysis Set
14.5.1.1	Laboratory Test Results – Glucose Metabolism: Full Analysis Set
14.5.1.2	Laboratory Test Abnormal Results – Glucose Metabolism: Full Analysis Set
14.5.2.1	Laboratory Test Results – Endocrinology: Full Analysis Set
14.5.2.2	Laboratory Test Abnormal Results – Endocrinology: Full Analysis Set
14.5.3.1	Laboratory Test Results – Lipid Metabolism: Full Analysis Set
14.5.3.2	Laboratory Test Abnormal Results – Lipid Metabolism: Full Analysis Set
14.5.4.1	Laboratory Test Results – Clinical Chemistry: Full Analysis Set
14.5.4.2	Laboratory Test Abnormal Results – Clinical Chemistry: Full Analysis Set
14.5.5.1	Laboratory Test Results – Hematology: Full Analysis Set

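### Table 14.5.2.2 (SAP 9.6) is a yearly prevalence count that cannot by itself tell newly abnormal thyroid or cortisol results from known, replaced deficiencies

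*SAP*

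**What the plan says.** **Who is enrolled.** Protocol 4.1 admits pre-pubertal children "with either isolated GHD, or GH insufficiency as part of multiple pituitary hormone deficiency". Item 9 adds: "Children with multiple hormonal deficiencies must be on stable replacement therapies for other hypothalamo-pituitary-organ axes for at least 3 months", with six months for thyroid replacement. Neither document says how many such children were enrolled or entered the OLE.

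**Why the hormones are followed.** Protocol 5.7.1.4 states: "Blood TSH and T4 should be monitored throughout the study since GH treatment may unmask previously undiagnosed or sub-clinical central hypothyroidism". It gives the parallel reason for cortisol, namely unmasked central hypoadrenalism. SAP 3.2.1 lists thyroid status and cortisol as safety endpoints 7 and 9, and safety is the primary objective of the OLE analysis (SAP 3.1.1).

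**How they are tabulated.** SAP 9.6 states: "Summary of abnormal results (reported as low, high, clinically significant) will be provided for each 12 month period". Its denominator is everyone who starts the period, whatever their endocrine status. SAP 5 says that "all patients will be included in a single Full Analysis Set for reporting". The resulting output is Table 14.5.2.2, "Laboratory Test Abnormal Results – Endocrinology: Full Analysis Set". For changes, as distinct from counts, SAP 9.6 says: "Changes within each 12 month period will use the first visit of the 12 month period as the baseline".

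**What the protocol foresaw.** For laboratory and ECG data, Protocol 8.5 mentions, if appropriate, shift tables from baseline to the most extreme later value. The SAP table list has a shift table for ECG only (14.6.3.2).

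**The concern.** The monitoring question is about new events: does a child whose thyroid or adrenal axis was thought intact become abnormal on GH? The planned count answers a different question: how many children have an out-of-range value this year, whatever their history. A child with a known deficiency on replacement can be flagged in any year with no change in status, and a persistent abnormality can be counted again in each period.

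The protocol itself keeps the two groups apart. Appendix 7 asks for follow-up cortisol in all patients, with or without pre-existing central hypoadrenalism, and reserves repeat ACTH testing for suspected new disease. The SAP table does not carry that distinction. At stake is whether two declared safety endpoints get a summary from which a reader can see new abnormalities without rebuilding each patient's history from listings.

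**Working it through.** The plan states no rate, power or sample size for this table, so there is no figure to reproduce. The check sets the sections side by side and then shows, under assumption, how far the count could depart from new cases.

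**1. Does any condition remove known disease from the count?** SAP 9.6 conditions neither the numerator nor the denominator on baseline status, medical history or concomitant replacement. SAP 5 defines one analysis set. The answer is no.

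**2. Do other planned outputs show new abnormalities?**

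| Output | What it catches | What it leaves |
|---|---|---|
| Adverse events of special interest (SAP 9.1; Tables 4.1, 14.3.2.5, 20) | Thyroid dysfunction and adrenal cortical hypofunction starting in the period. Under Protocol 7.1 an abnormal value is an adverse event if it causes signs or symptoms, is clinically significant or needs therapy | Sub-clinical shifts that meet none of these. Worsening of known disease also qualifies, so the tables are not purely new onset |
| Concomitant medications (SAP 9.12; Table 14.6.4) | Any replacement used in the year | First starts: a child on thyroxin since entry appears every year |
| Within-period change (SAP 9.6) | Mean movement within the year | Status at study entry, because the baseline resets each year |
| Medical history, endocrinology and medication data (SAP 8.4; Listings 16.2.8.5, 16.2.9.4) | Everything, patient by patient | Any summary |

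The uncovered part is therefore mainly sub-clinical shifts not reported as adverse events.

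**3. How far could the count depart from new cases?** N = 53 started the OLE (SAP 4.1). The other inputs are assumptions, because the documents give none of them:
- m: share of children with a known, replaced deficiency
- a: yearly chance that such a child has an out-of-range value
- u: yearly rate of new abnormality in the rest

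Flagged with known disease = 53 × m × a. Newly flagged = 53 × (1 − m) × u. Table percentage = the sum of the two / 53. Background out-of-range values in healthy children are ignored.

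| m | a | u | Known, flagged | New, flagged | Table shows | Share that is new |
|---|---|---|---|---|---|---|
| 0% | n/a | 5% | 0 | 53 × 0.05 = 2.65 | 5.0% | 100% |
| 10% | 30% | 5% | 53 × 0.1 × 0.3 = 1.59 | 53 × 0.9 × 0.05 = 2.39 | 7.5% | 60% |
| 20% | 50% | 5% | 53 × 0.2 × 0.5 = 5.30 | 53 × 0.8 × 0.05 = 2.12 | 14.0% | 29% |
| 40% | 80% | 2% | 53 × 0.4 × 0.8 = 16.96 | 53 × 0.6 × 0.02 = 0.64 | 33.2% | 4% |

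The share of flags that are new runs from 4% to 100% over these inputs. This gives the direction of the effect; it is not an estimate for this trial. A count restricted to children at risk would return u itself, 2% or 5% here.

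**4. Which baseline should define at risk?** The SAP covers only Periods III to V (SAP 2), after 12 months of somatrogon or Genotropin. If children were split only by status at Period I baseline, a child found deficient and treated in Periods I–II would sit in the no-deficiency group. That child could be flagged in every OLE year, and would be missed by a count of first starts during the OLE. Status at OLE start avoids this. Period I baseline is still needed to show the whole shift since before GH.

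**The case against.** The strongest reply is that new deficiencies are already reported as such. A child whose hypothyroidism is found and treated meets the Protocol 7.1 definition of an adverse event and should enter the thyroid table, which counts events starting in the period. A later normal T4 does not erase an earlier abnormal value within the same 12-month summary. Protocol 8.5 itself asks for the number of patients outside normal values for cortisol and the thyroid panel, so the table follows the protocol, and the shift tables were only to be given if appropriate. The OLE is descriptive, and endocrinology and medication listings are planned.

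Most of this stands. A reader might infer that the plan hides newly unmasked deficiencies. The documents do not support that: the limitation belongs to one table, and clinically recognised cases have their own route.

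A reader might also infer that known disease is in fact counted every year. That is not established either. The table counts out-of-range results, not diagnoses. Protocol 5.7.1.4 has thyroid replacement adjusted towards mid-range T4, which applies to known as well as new cases. It states no such target for TSH or cortisol, so such children can be flagged, but how often is unknown.

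What the reply leaves open is the sub-clinical shift, which Protocol 5.7.1.4 names as a reason for monitoring. It is only partly covered by visit summaries, yearly changes and listings.

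**Conclusion.** The point holds in a limited form. Table 14.5.2.2 is a yearly prevalence count over all patients. It can include children with a known, replaced deficiency each year, and it cannot alone separate them from newly abnormal children. The gap left after the adverse event tables is mainly sub-clinical shifts.

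The size cannot be fixed. The documents give no number of children with multiple deficiency in the OLE; it could be near zero, in which case the table would do little harm. The percentages in the working rest wholly on assumed inputs.

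Two further inferences should be avoided. Splitting the table would not show whether somatrogon causes unmasking, since the OLE has no concurrent daily-GH comparator and no hypothesis test. And T3 is not collected throughout: the protocol's Period V schedules list TSH, free T4 and cortisol only, although the SAP's first-year PEN chart still lists T3.

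This is a reporting gap of moderate weight on two declared safety endpoints. No test, power or sample size is affected.

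**What to change.** Amend SAP 9.6 and the table list, for TSH, FT4, cortisol and, where collected, T3:

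1. Add a shift display to the most extreme value, from Period I baseline and from OLE start, as Protocol 8.5 foresaw.
2. Count new abnormalities per period among children who, at OLE start, were normal for that parameter and had no known deficiency of, or replacement for, that axis. Use these children as the denominator.
3. Show the other children separately, distinguishing deficiency known at Period I baseline from deficiency first found or treated in Periods I–II.
4. Report first starts of thyroid or glucocorticoid replacement during the OLE, from the existing concomitant medication data.

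The existing Table 14.5.2.2 can stay, labelled as prevalence. Pituitary deficiencies and medications were recorded at screening (Protocol 5.1.1), and the hormones were measured at Visit 1 and Month 12, so no new assessment is needed and no clinical rule changes. The cost is smaller subgroups and a little more programming.
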